11.0 Treatment Evaluation

The International Myeloma Working Group (IMWG) uniform response criteria (Rajkumar et al, 2011) will be used to assess response to therapy

11.1 Terms and definitions

- **M-protein:** synonyms include M-spike, monoclonal protein and myeloma protein, paraprotein, M-component.

Serum M-protein level is quantitated using densitometry on SPEP except in cases where the SPEP is felt to be unreliable.

- M-proteins migrating in the β -region (usually IgA M-proteins)
- Cases in which the M-protein is so large and narrow on agarose (some specimens >4 g/dL) that they underestimate the actual immunoglobulin level (by greater than 1500 mg/dL) due to technical staining properties of the agarose gel.
- Cases in which there are multiple peaks of same M-protein (aggregates or dimers)

If SPEP is not available or felt to be unreliable (above examples) for routine M-protein quantitation, then quantitative immunoglobulin levels derived from nephelometry or turbidometry can be accepted. However, this must be explicitly reported at baseline, and only nephelometry can be used for that patient to assess response. SPEP derived M-protein values and quantitative nephelometric immunoglobulin values cannot be used interchangeably.

Urine M-protein measurement is estimated using 24-h UPEP only. Random or 24 h urine tests measuring kappa and lambda light chain levels are not reliable and are not recommended.

FLC estimation is currently carried out using the serum FLC assay (Freelite, The Binding Site Limited, UK). Patients with kappa/lambda FLC ratio <0.26 are defined as having monoclonal lambda FLC and those with ratios >1.65 as having a monoclonal kappa FLC. The monoclonal light chain isotype is considered the involved FLC isotype, and the opposite light chain type as the uninvolved FLC type.

- **Response terms:** The following response terms will be used: stringent Complete Response (sCR), complete response (CR), very good partial response (VGPR), partial response (PR), Minimal Response (MR), stable disease (SD), and progressive disease (PD).

In addition, for each response category, there will be an “unconfirmed” response category, which will be for internal use, for the purpose of guiding decision making and test ordering. These designations will be applied at the time of the first measurement at which the quantitative aspect of the response category has been satisfied without the confirmation step having been satisfied. The designation “u” will precede the standard abbreviations, and will include usCR, uCR, uVGPR, uPR, uMR, uPD.

- **Measurable disease:** Patients who have a measurable serum or urine M-protein.
 - serum M-protein >1 g/dL OR urine M-protein >200 mg/24 hr

11.2 Clarification of test indications

Listed below are the minimal required tests required to assess response based on the characteristics of their disease at on study.

Table 11.2				
Tests Required To Assess Response (Must Be Done At Each Disease Measurement Visit except as indicated^{1,2})				
On Study Baseline Value	SPEP³	24 hr UPEP²	Ig FLC	BM Bx
Serum M-protein ≥ 3 g/dl, and urine M-protein ≥ 500 mg/24 hrs	X	X		
Serum M-protein ≥ 3 g/dl, but urine M-protein < 500 mg/24 hrs	X			
Serum M-protein < 3 g/dl, and urine M-protein ≥ 500 mg/24 hrs		X		

¹ **SPEP, UPEP, Immunofixation studies of both serum and urine, and Bone marrow biopsy** are required to document CR regardless of registration values, and in addition **FLC** measurement and **bone marrow immunophenotyping** is required to document sCR. SPEP and UPEP are required to document VGPR regardless of registration values.

² For serum measurable patients, 24 hour urine does not need to be confirmed (i.e. repeated after documented response) for any response category

³ If serum M-protein is being followed by quantitative immunoglobulin levels derived from nephelometry or turbidometry, quantitative immunoglobulins are required. SPEP is only required to document CR or VGPR.

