3.1 Inclusion Criteria

3.11 Age ≥ 18 years.

3.12 The following laboratory values obtained ≤ 7 days prior to registration.

- Absolute neutrophil count (ANC) $\geq 1700/\text{mm}^3$
- Platelet count $\geq 100,000/\text{mm}^3$
- Hemoglobin ≥ 8.0 g/dL
- SGOT (AST) ≤ 3 x upper limit of normal (ULN)
- Creatinine clearance ≥ 30 mL/min (as determined by Cockcroft-Gault equation*)

*Cockcroft-Gault Equations:

$$\text{Creatinine clearance for males} = \frac{(140 - \text{age})(\text{actual body weight in kg})}{(72)(\text{serum creatinine in mg/dL})}$$

$$\text{Creatinine clearance for females} = \frac{(140 - \text{age})(\text{actual body weight in kg})(0.85)}{(72)(\text{serum creatinine in mg/dL})}$$

Example: A woman aged 75, weight 50 kg and creatinine of 1.35 mg/dL has a calculated clearance of 28.

3.13 Diagnosis of multiple myeloma according to International Myeloma Working Group criteria and one of the following:

- SMM
- IMM
- newly diagnosed MM

Note: Patients with lytic disease and anemia are eligible

3.14 High risk disease defined by all of the following:

- $\geq 10\%$ bone marrow plasma cells
AND
- Abnormal serum free light chain (FLC) ratio (< 0.26 or > 1.65) by serum FLC assay
AND
- Monotypic Plasma Cell S-phase $\geq 0.3\%$

3.15 Measureable level of M-protein > 1 g/dL on serum protein electrophoresis or > 200 mg of M-protein on a 24 hour urine protein electrophoresis.

3.16 Negative tuberculosis (TB) testing (Quantiferon – TB blood test or skin test) ≤ 7 days prior to registration.

3.17 ECOG performance status (PS) 0, 1 or 2 ([Appendix I](#)).

- 3.18 Provide signed informed consent.
- 3.19a Negative (serum or urine) pregnancy test done ≤ 7 days prior to registration, for women of childbearing potential only.
NOTE: A second pregnancy test must be performed within 24 hours prior to the start of lenalidomide. The subject may not receive lenalidomide until the study doctor has verified that the results of these pregnancy tests are negative.
- 3.19b Willing to return to enrolling institution for follow-up (during the Active Monitoring Phase of the study).
- 3.19c Willing and able to comply with the requirements of the Revlimid REMS™ program.
- 3.19d Females of childbearing potential must be willing to adhere to the scheduled pregnancy testing as required by the Revlimid REMS™ program.
- 3.2 Exclusion Criteria
- 3.21 Prior treatment with any other agent that may affect M-protein ≤ 30 days prior to registration.

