11.3 Confirmed response

In order to be classified as a hematologic response, confirmation of serum M- protein, serum immunoglobulin free light chain (when primary determinant of response) and urine M- protein (when primary determinant of response) results must be made by verification on two consecutive determinations.

- Bone marrow aspirate and biopsy are **only** required to document CR or sCR, except for patients with evaluable disease **only**, where a bone marrow is required to document all response categories including progression. However, a second confirmatory bone marrow is **not** required to confirm response in any case.
- Radiographic studies are not required to satisfy these response requirements; however, if radiographic studies were performed there should be no evidence of progressive or new bone lesions.

Appropriate tests required to document and confirm response are listed in Table 11.2

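### Do the 3 g/dL and 500 mg/24 h cut-offs in Table 11.2 leave some patients without the tests needed to grade a partial response?

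*Combined protocol and SAP*

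**What the plan says.** Inclusion criterion 3.15 asks for a "Measureable level of M-protein > 1 g/dL on serum protein electrophoresis", or more than 200 mg on a 24-hour urine collection. Section 11.1 repeats these limits as the definition of measurable disease, "serum M-protein >1 g/dL OR urine M-protein >200 mg/24 hr", and descriptive factor 12.4 uses them to record which protein is followed, with a category for both.

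Table 11.2 lists the minimum tests for assessing response and uses different limits. The row "Serum M-protein ≥ 3 g/dl, but urine M-protein < 500 mg/24 hrs" marks SPEP only. The row "Serum M-protein < 3 g/dl, and urine M-protein ≥ 500 mg/24 hrs" marks UPEP only. The row with both values at or above the limits marks both tests. Footnote 1 adds that "SPEP and UPEP are required to document VGPR regardless of registration values", and it asks for both tests for CR as well. Footnote 2 says "For serum measurable patients, 24 hour urine does not need to be confirmed".

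Section 11.3 says of serum M-protein, and of FLC and urine where they drive the response, that "results must be made by verification on two consecutive determinations". It closes with "Appropriate tests required to document and confirm response are listed in Table 11.2".

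Table 11.5 requires a serum and a urine reduction for PR and for MR, for whichever proteins were present at baseline. Its footnote c says that when more than one protein is measurable at baseline both are followed, and otherwise only the measurable one.

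The Section 4.0 test schedule orders SPEP and 24-hour UPEP for all patients at baseline, at the end of Cycles 1 to 3, after every third cycle from then on, and at the end of treatment.

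**The concern.** Two sets of cut-offs for the same measurements look like an error with consequences. A patient can have both proteins measurable under 11.1 and still fall in a Table 11.2 row that lists one test. Section 11.3 points to that table for documenting and confirming response, and footnote 1 restores the second test for CR and VGPR but not for PR or MR. A site that took the table as sufficient could call a PR from one protein while the other had barely moved.

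PR counts towards the overall response rate in 16.332 and the phase I response profile in 16.233. In the row with urine at or above 500 mg, confirmation looks awkward too: footnote 2 may waive the urine repeat while the row lists no serum test.

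**Working it through.** The documents state no figure for this point, so the check compares the tests listed with the tests needed.

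**Step 1: baseline groups.** Cross serum (up to 1, >1 to <3, ≥3 g/dL) with urine (up to 200, >200 to <500, ≥500 mg/24 h). Eight of the nine cells are eligible under 3.15. The tests needed follow from 11.1 and Table 11.5 footnote c.

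| Serum (g/dL) | Urine (mg/24 h) | Needed | Table 11.2 | Section 4.0 |
|---|---|---|---|---|
| ≥3 | ≥500 | both | both | both |
| ≥3 | >200 to <500 | both | SPEP | both |
| ≥3 | ≤200 | SPEP | SPEP | both |
| >1 to <3 | ≥500 | both | UPEP | both |
| ≤1 | ≥500 | UPEP | UPEP | both |
| >1 to <3 | >200 to <500 | both | no row | both |
| >1 to <3 | ≤200 | SPEP | no row | both |
| ≤1 | >200 to <500 | UPEP | no row | both |

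Two cells have both proteins measurable and one test listed. Three cells match no row in the available text; rows may have been lost when the table was read from PDF, so nothing is built on that. The last column covers the needed tests in all eight cells.

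**Step 2: grading with the scheduled results.** Two hypothetical patients, one from each affected group:

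- Baseline 2.0 g/dL and 600 mg; follow-up 1.8 g/dL and 150 mg. Serum fall (2.0 − 1.8)/2.0 = 10%; urine fall (600 − 150)/600 = 75%, to below 200 mg. The urine part of PR is met. The serum part, 2.0 × 0.5 = 1.0 g/dL or less, is not. Not PR.
- Baseline 3.5 g/dL and 450 mg; follow-up 1.70 g/dL and 400 mg. Serum fall (3.5 − 1.70)/3.5 = 51.4%; urine fall (450 − 400)/450 = 11.1%. The serum part is met. The urine part, below 200 mg (the 90% alternative, 45 mg, lies inside that), is not. Not PR.

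Section 4.0 puts both results in hand at the evaluation and Table 11.5 gives the right grade each time. The wrong grade needs someone to set aside a scheduled result and footnote c.

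**Step 3: confirmation when serum is >1 to <3 g/dL and urine ≥500 mg.** If serum measurable in footnote 2 means more than 1 g/dL, the urine repeat is waived and 11.3 still requires the serum to be verified. If it means 3 g/dL or more, the urine is repeated, and the serum is still verified under 11.3. On either reading the next scheduled evaluation supplies what is needed, and Table 11.5 footnote a lets it confirm at any time before new therapy. The longest scheduled gap is 3 × 28 = 84 days, give or take the visit window. The response rate carries no time limit, so waiting costs nothing.

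**Step 4: size if the schedule were ignored.** With 45 evaluable patients per arm, one misgraded PR moves that arm's rate by 1/45 = 2.2 percentage points, and three by 3/45 = 6.7. The documents give no baseline M-protein distribution and no reason to expect scheduled results to be discarded, so a count of 0 to 3 per arm is pure assumption. Zero is what the plan as written implies.

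**Step 5: primary endpoint.** PD may be called on either protein. Both are measured at the same evaluations, so no effect on TTP, the 52 events or the 80% power is shown.

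**The case for a change.** The best argument for amending is that Table 11.2 is not decorative. Its header makes the listed tests compulsory at each disease measurement visit, and 11.3 names it as the source for documenting and confirming response. Footnote 1 restores both tests for CR and VGPR only, which invites the inference that one test is enough for PR. An off-schedule repeat ordered from the table could include one test. Aligning the cut-offs would cost almost nothing.

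The textual conflict stands, and so do the two groups. The inference does not. A minimum is not breached by a fuller schedule, and footnote c, which is attached to PR and MR, settles which proteins are followed. An off-schedule repeat with one test leaves the response unconfirmed until the next evaluation, which has both. The confirmation difficulty is the same cut-off mismatch seen from another side.

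A repair can also do harm. A rule that PR, MR and PD must all be graded on both SPEP and UPEP would contradict footnote c for patients with one measurable protein, the either-protein rule for PD, and the rule in 11.1 that patients followed by nephelometry are assessed by nephelometry only.

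**Conclusion.** No change follows, because there is no gain. Table 11.2 carries cut-offs that do not match 3.15, 11.1 and 12.4, and two eligible groups are listed for one test where they need two. That is a minor inconsistency of wording. Section 4.0 already orders both tests for everyone, Table 11.5 already grades on both where both are measurable, and 11.3 already requires serum confirmation. Correcting the table would alter no scheduled test, no endpoint definition and no conclusion.

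This rests on two assumptions: that sites follow the Section 4.0 schedule, and that analysts grade from Table 11.5. Both are what the protocol instructs. If they failed, the effect would be 2.2 percentage points per misgraded PR in one arm, on a secondary endpoint compared in an exploratory way, with no reason to expect the arms to differ. If the protocol is amended for other reasons, the cut-offs can be reconciled then, after a check against the source table.

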11.3 Confirmed response

In order to be classified as a hematologic response, confirmation of serum M- protein, serum immunoglobulin free light chain (when primary determinant of response) and urine M- protein (when primary determinant of response) results must be made by verification on two consecutive determinations.

- Bone marrow aspirate and biopsy are **only** required to document CR or sCR, except for patients with evaluable disease **only**, where a bone marrow is required to document all response categories including progression. However, a second confirmatory bone marrow is **not** required to confirm response in any case.
- Radiographic studies are not required to satisfy these response requirements; however, if radiographic studies were performed there should be no evidence of progressive or new bone lesions.

Appropriate tests required to document and confirm response are listed in Table 11.2

11.4 Bone progression

Caution must be exercised to avoid rating progression on the basis of variation of radiologic technique alone. Compression fracture does not exclude continued response and may not indicate progression. When progression is based on skeletal disease alone, it should be discussed with the Study Chair before removing the patient from the study.

11.5 Response and Progression

Criteria for response and progression are listed in Table 11.5. Progressive disease for all patients as defined in Table 11.5.

Table 11.5	
CATEGORY	RESPONSE CATEGORY ^a
Stringent Complete Response (sCR) ^b	
 • CR as defined plus • Normal FLC ratio and • Absence of clonal PCs by immunohistochemistry or 2- to 4- color flow cytometry ^h
Complete Response (CR) ^b	
 • Negative immunofixation of serum and urine ^c and • Disappearance of any soft tissue plasmacytoma and <5% PCs in Bone Marrow
Very Good Partial Response (VGPR)	
 • Serum and urine M-protein detectable by immunofixation but not on electrophoresis ^c or • $\geq 90\%$ reduction in serum M-protein and urine M-protein <100 mg/24 h ^c
Partial Response (PR)	
 • If present at baseline, $\geq 50\%$ reduction of serum M-protein and reduction in 24-hour urinary M-protein by $\geq 90\%$ or to <200 mg/24hrs ^c • If present at baseline, $\geq 50\%$ reduction in the size of soft tissue plasmacytomas
Minor Response (MR)	
 • If present at baseline, $\geq 25\%$ but $\leq 49\%$ reduction of serum M protein and reduction in 24-hour urine M-protein by 50-89% which still exceeds 200mg/24 hours ^c and • If present at baseline, 25-49% reduction in the size of soft tissue plasmacytoma and • No increase in the size or number of lytic bone lesions (development of compression fracture does not exclude response)
Progressive Disease (PD) ^{b, g}	
Increase of 25% from lowest value in any of the following ^{e, f}:
 
 • Serum M-protein (absolute increase must be ≥ 0.5 g/dL) and/or • Urine M-protein (absolute increase must be ≥ 200 mg/24 hrs) and/or 
Or any one or more of the following:
 
 • Development of new bone lesion or soft tissue plasmacytoma or definite increase in the size of existing bone lesions or soft tissue plasmacytoma • Development of hypercalcemia (corrected serum calcium > 11.5mg/dL) that can be attributed solely to the PC proliferative disorder
Stable Disease (SD)	Not meeting criteria for sCR, CR, VGPR, PR, MR or PD

^a All response categories require two consecutive assessments (sCR, CR, VGPR, PR, MR, PD) made at any time before the institution of any new therapy; sCR, CR, VGPR, PR, MR and SD categories also require no known evidence of progressive or new bone lesions if radiographic studies were performed. Radiographic studies are not required to satisfy these response requirements. Bone marrow assessments need not be confirmed. Each category, except for stable disease, will have a working subcategory of “unconfirmed” [prefix ‘u’] to designate first time point at which response category MAY have been achieved if confirmed.

^b CR patient will need to progress at the same level as VGPR and PR patients to be considered a PD. A positive immunofixation alone is not sufficient.

^c If more than one M protein spike meets the criteria for measurable disease at baseline, then both need to be followed for response. Otherwise, only follow the measurable M protein spike for response.

^d In patients in whom the only measurable disease is by serum FLC levels: CR in such patients indicates a normal FLC ratio of 0.26-1.65 in addition to the CR criteria listed above.

^e A "25% increase" refers to M protein, FLC and bone marrow results and does not refer to bone lesions, soft tissue plasmacytoma or hypercalcemia. The lowest value does not need to be a confirmed value. If the lowest serum M-protein is ≥ 5 g/dL, an increase in serum M-protein of ≥ 1 g/dL is sufficient to define disease progression.

^f In the case where a value is felt to be a spurious result per physician discretion (for example, a possible lab error), that value will not be considered when determining the lowest value.

^g Progressive disease should be confirmed. However, treatment may be discontinued for progressive disease that is unconfirmed per physician discretion. In this case, an objective status of PD should be entered on the measurement form and progressive disease should be reported on the event monitoring form.

^h Presence/absence of clonal cells is based upon the k/l ratio. An abnormal k/l ratio by immunohistochemistry requires a minimum of 100 plasma cells for analysis. An abnormal ratio reflecting presence of an abnormal clone is k/l of 4:1 or 1:2.

12.0 Descriptive Factors

- 12.1 Prior treatment: Yes vs. no.
- 12.2 Durie Salmon Stage of myeloma at diagnosis: I vs. II vs. IIIa vs. IIIb
- 12.3 ISS Stage of myeloma at diagnosis: I vs. II vs. III
- 12.4 Parameters followed for hematologic response (pick one): serum M- protein >1 g/dL and urine M-protein >200 mg/24 hours vs. serum M-protein >1 g/dL only vs. urine M-protein >200 mg/24 hours only.
NOTE: Distinguish between SPEP measurements versus quantitative IgA measurements for serum M-protein
- 12.5 Diagnosis: Smoldering multiple myeloma (SMM) vs. indolent multiple myeloma (IMM) vs. newly diagnosed multiple myeloma
- 12.6 Dose Level: 1 vs. 2 vs. 3

13.0 Treatment/Follow-up Decision at Evaluation of Patient

NOTE (Phase I Only): As of Addendum 5, Anakinra will no longer be provided and all patients will go off study treatment. Event monitoring will no longer be required. Patients may obtain Anakinra commercially and be treated off study

- 13.1 Responding to treatment
Patients who are sCR, CR, VGPR, PR, or SD (or usCR, uCR, uVGPR, uPR) will continue treatment per protocol.
- 13.2 Treatment continuation
In the absence of treatment delays due to adverse event(s), treatment may continue until one of the following criteria applies:
 - 13.21 Progression requiring treatment for active myeloma
 - 13.22 Unacceptable toxicity and ineligibility for retreatment.
 - 13.23 Patient refusal of continued treatment.

All attempts should be made to complete the End of Study procedures if a patient withdraws from the trial early. The patient will then go to event monitoring per Section 18.0.

13.3 Ineligible patients

A patient is deemed ineligible if at the time of registration, the patient did not satisfy each and every eligibility criteria for study entry. The patient may continue treatment off protocol at the discretion of the physician as long as there are no safety concerns, and the patient was properly registered. The patient will go directly to the event-monitoring phase of the study.

- If the patient received treatment, all data up until the point of confirmation of ineligibility must be submitted. Event monitoring will be required per section 18.0 of the protocol.
- If the patient never received treatment, on-study material and the End of Active Treatment/Cancel Notification Form must be submitted. No further data submission is necessary.

13.4 Major Violation

A patient is deemed a major violation, if protocol requirements regarding treatment in Cycle 1 of the initial therapy are severely violated that evaluability for primary end point is questionable. All data up until the point of confirmation of a major violation must be submitted. The patient will go directly to the event-monitoring phase of the study. Event monitoring will be required per Section 18.0 of the protocol.

The patient may continue treatment with lenalidomide and dexamethasone off-protocol at the discretion of the physician as long as there are no safety concerns, and the patient was properly registered. Event monitoring will be required per Section 18.0 of the protocol.

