16.11 Primary Endpoint

The primary endpoint of the phase I portion is toxicity, and more specifically, MTD determination. The primary endpoint of the phase II portion of this study is time to disease progression (TTP), which will be compared between the two arms. Time to progression is defined as the time from registration until the earliest date of documentation of disease progression. If a patient dies without a documentation of disease progression, the patient will be considered to have had disease progression at the time of their death unless there is sufficient documented evidence to conclude no progression occurred prior to death. If a patient receives subsequent treatment before disease progression, they will be censored on the date of the last disease assessment. All patients meeting the eligibility criteria who have signed a consent form and have begun treatment will be evaluable for the primary endpoint.

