16.12 Sample Size

The phase I portion of the trial is expected to require at least 12 patients and as many as 18 patients to determine the MTD. The phase II portion of this study is expected to accrue a maximum of 45 evaluable patients in each arm unless undue toxicity is encountered. We anticipate accruing 12 additional patients (2 phase I, 5 phase II in each arm) to account for ineligibility, cancellation, major treatment violation, or other reasons. Therefore, this study is expected to accrue a maximum of 120 patients overall.

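### Sections 13.4 and 16.12 leave it open whether phase II patients with a severe Cycle 1 treatment violation count for TTP, while Sections 16.11 and 16.31 say that they do

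*Combined protocol and SAP*

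**What the plan says.** - **Section 13.4 (Major Violation).** The label applies if "protocol requirements regarding treatment in Cycle 1 of the initial therapy are severely violated that evaluability for primary end point is questionable". The section is not restricted by phase, whereas Section 13.6, on failure to complete Cycle 1, is marked phase I only. On data: "All data up until the point of confirmation of a major violation must be submitted". On follow-up: "The patient will go directly to the event-monitoring phase of the study. Event monitoring will be required per Section 18.0 of the protocol". It adds: "The patient may continue treatment with lenalidomide and dexamethasone off-protocol at the discretion of the physician".
- **Section 16.12 (Sample Size).** The phase II target is 45 evaluable patients per arm. A further 5 per arm are planned "to account for ineligibility, cancellation, major treatment violation, or other reasons".
- **Section 16.11 (Primary Endpoint).** "All patients meeting the eligibility criteria who have signed a consent form and have begun treatment will be evaluable for the primary endpoint". Section 16.31 repeats the sentence. Neither makes an exception for major violations.
- **Section 16.11, censoring.** "If a patient receives subsequent treatment before disease progression, they will be censored on the date of the last disease assessment". The kind of treatment meant is not defined.
- **Section 18.13.** Event monitoring is every 6 months until progression, with documentation of progression submitted. It ends 3 years after registration.

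**The concern.** Questioning evaluability because of Cycle 1 treatment makes sense in phase I, where the endpoint is Cycle 1 toxicity. In phase II the endpoint is TTP in a randomized comparison, and a patient's Cycle 1 treatment does not affect whether TTP can be observed. An exclusion on that ground would depend on events after randomization. Severely violated has no objective phase II criterion, so the classification would be discretionary. If violators differ in prognosis from other patients, and violations differ between arms, the TTP comparison is biased. The response comparison is exposed too, because Section 16.332 divides by the number of evaluable patients.

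The ambiguity also affects who makes up the 45 per arm. Section 16.35 keeps patients beyond the target number out of decision making, so counting or not counting a violator can change which later patients enter the primary test.

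Keeping the violators leaves two further gaps: less detailed follow-up, and a censoring rule that may or may not apply to them.

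**Working it through.** **1. The plan's own design.** Inputs from Section 16.31: medians 20 and 40 months (hazard ratio 2), one-sided 0.05, 80% power, 1:1, 45 per arm, 24-month accrual, 24-month minimum follow-up.

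- Events (Schoenfeld): 4(1.645 + 0.842)²/(ln 2)² = 51.5, rounded up to 52. Power at 52 events: Φ(√52 × 0.693/2 − 1.645) = 0.804.
- Probability of an event by month 48, with λ = ln 2/median: 1 − (e^(−24λ) − e^(−48λ))/(24λ). Control (24λ = 0.832): 0.704. Experimental (24λ = 0.416): 0.460.
- Expected events: 45 × 0.704 + 45 × 0.460 = 31.7 + 20.7 = 52.4.

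The stated 52 events and 80% power reproduce.

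**2. The sections side by side, for an eligible, treated phase II violator.**

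| Section | Evaluable for TTP? |
|---|---|
| 13.4 | Questionable; no analysis rule given |
| 16.12 | By implication no, since extra accrual beyond the evaluable target is planned for this reason |
| 16.11, 16.31 | Yes |

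Section 13.4 also handles violators much as Section 13.3 handles treated ineligible patients: data up to confirmation, then event monitoring. Ineligible patients are outside the Section 16.11 set, so the parallel invites the reading that violators are outside it too.

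**3. Follow-up if they are kept.** After Cycle 3, Section 4.0 schedules serum and urine protein electrophoresis every third cycle, or 3 × 28 = 84 days. Event monitoring reports come every 6 months and prescribe no tests. With the analysis at month 48, a violator registered in the first 12 months of accrual passes the 3-year limit before the analysis, by up to 48 − 36 = 12 months.

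**4. Power if violators contribute nothing.** The documents give no violation rate, so the numbers here are assumptions. The upper end of 5 per arm is the whole Section 16.12 allowance (5/50 = 10%), which also covers ineligibility, cancellation and other reasons. If 2 of 45 per arm contribute nothing: 50.1 events, power 0.790. If 5 of 45: 46.6 events, power 0.764. If 50 per arm are randomized and 5 dropped, 45 remain and power is about 0.80 to 0.81.

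**5. Power with dilution.** Log-rank simulation, 8,000 runs per cell. Experimental-arm violators are assumed to have the control hazard throughout.

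| Randomized per arm | Violators per arm | Kept, full follow-up | Censored at about 3 cycles | Dropped |
|---|---|---|---|---|
| 45 | 0 | 0.797 | – | – |
| 45 | 2 | 0.767 | 0.782 | 0.794 |
| 45 | 5 | 0.713 | 0.752 | 0.753 |
| 50 | 5 | 0.766 | 0.798 | 0.808 |

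**6. Type I error under informative removal.** Null hypothesis, 50 per arm, 5 patients in each arm at twice the hazard. Violations are assumed to occur only in the experimental arm, in exactly those 5. One-sided type I error (nominal 0.05) is 0.046 if they are kept with full follow-up, 0.082 if censored at 1 month, and 0.084 if dropped. Replacement restores the number of patients but does not remove this bias.

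**The case against.** The strongest reply is that only one explicit rule governs the primary analysis. It is stated twice in the statistical section and keeps these patients. Section 13.4 raises a doubt and contains no exclusion, and Section 16.12 is an accrual allowance, not an analysis-set definition. That is correct, and it makes Section 16.11 the better reading. It does not explain why violators are budgeted as additional to the evaluable patients, and no section says which text prevails.

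Four stronger readings are tempting, and the documents do not support them.

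- *A reader might infer that violators are declared not evaluable.* Section 13.4 says only that evaluability is questionable.
- *A reader might infer that kept violators have almost no follow-up.* Section 13.4 requires event monitoring, and Section 18.13 sets it every 6 months to progression for up to 3 years. Censoring near entry follows only if off-protocol lenalidomide/dexamethasone counts as subsequent treatment. Section 13.4 speaks of continuing those drugs, which reads more naturally as ongoing therapy; the text does not settle it.
- *A reader might infer that the rule removes those who tolerated anakinra worst.* Syringes omitted under Section 8.3 are compliance, not violation. The notes closing Section 8 keep a patient on study while any agent continues, and refusal falls under Section 13.23. Injection-site reactions, which Section 1.3 places in the first month and Section 15.37 puts above 10%, make unequal violation rates possible, but no text shows them.
- *A reader might infer that 10% per arm could be lost to violations.* That figure pools all reasons, and ineligible and cancelled patients are outside the evaluable set anyway.

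It also stands that the type I error result depends on a deliberately one-sided scenario.

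**Conclusion.** The inconsistency is real and should be corrected. The composition of the primary TTP set depends on which section is followed, and one reading permits a discretionary post-randomization exclusion in phase II. The main risk is selection bias. The loss of power from missing patients is modest, and replacement would offset it.

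The size cannot be estimated from the documents. The figure of 0.08 for type I error shows what removal could do if violators were few (5 of 50), confined to the experimental arm and at twice the hazard. If violators were balanced between arms, or had ordinary prognosis, the bias would be smaller or absent; if they had better prognosis, it would run the other way. If Section 16.11 is followed, what remains is later and less certain dating of progression, the 3-year limit, and an unresolved censoring question.

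**What to change.** 1. Limit the evaluability wording in Section 13.4 to phase I, and delete major treatment violation from the phase II reasons in Section 16.12.
2. State in Sections 13.4 and 16.11 that eligible, treated phase II major violators stay in their randomized arm for the primary TTP and response analyses, and that progressions documented in event monitoring count as events.
3. State in Section 16.11 that lenalidomide/dexamethasone continued off protocol after a major violation is not subsequent treatment for censoring.
4. Preferably, keep collecting M-protein results on the Section 4.0 schedule until progression for these patients.
5. Use a per-protocol analysis without them only as a sensitivity analysis.

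The cost is wording, a few more routine test results, and some dilution. With 5 violators per arm, power is about 4 points lower if they are kept than if dropped, at equal numbers randomized (0.713 against 0.753 with 45 per arm; 0.766 against 0.808 with 50). If the target stays at 45 including violators, the comparison with dropping and replacing them is 0.713 against 0.808. With 2 violators of 45 it is 0.767 against 0.794 if dropped. These losses assume that experimental-arm violators gain nothing from anakinra. They are the price of keeping the comparison randomized.
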